2.2 REGISTRY SIZE AND DURATION

To document the clinical experience of the Plexa lead, the Plexa Registry is designed to follow 1271 subjects through the 60 month post-implant visit interval at up to 75 US sites.

2.3 SAMPLE-SIZE ANALYSIS

The investigation is designed to limit the number of subjects involved while still exposing the device to a sufficiently large patient population in order to ensure a representative and statistically meaningful sample.

The estimated sample size required to evaluate primary endpoint 1 is based on a superiority comparison of the overall Plexa lead AE-free rate to 92.5% at 5 years. The sample size for primary safety endpoint 1 was calculated based on the following assumptions:

Assumptions for primary safety endpoint 1

- Registry Design: nonrandomized registry
- Test basis: exact binomial test
- Type I error (alpha): 0.025 (one-sided for superiority)
- Statistical power: 80%
- Estimated AE-Free Rate at 5 years: 95.0% for Plexa leads
- Performance goal for AE-Free Rate at 5 years: 92.5%

For primary safety endpoint 1, a total of 750 evaluable Plexa leads would be required to demonstrate superiority to an AE-free rate of 92.5%. Assuming a 10% loss to follow-up rate per year over 5 years of follow-up (average of 8.2% of original population per year), a total of 1271 ($= 750 / 0.9^5$) subjects with an ICD lead would be required to be enrolled to evaluate primary safety endpoint 1.

2.3.1 Attrition

For the sample size calculation, a maximum loss to follow-up of 10% per year (41% over 5 years) was assumed. The attrition rate encompasses all causes for subject exits prior to study completion and will include any subject exits where the subjects are not replaced per Section 2.3.2.

2.3.2 Replacement of Subjects

A drop-out rate of 10% of subjects per year is expected in the Plexa Registry. The additional enrollment of 10% (total subject number: $n = 750 / 0.9^5$) is considered sufficient for the collection of the required primary endpoint 1 ($n = 750$). However, to ensure sufficient primary endpoint 1 evaluable data, subjects who exit the clinical investigation due to death, device explants, subject directed withdrawals, physician directed withdrawals, or loss of contact with the subject may be replaced as long as enrollment is ongoing. Subjects who have had a protocol defined adverse event will not be replaced. The subjects replaced will not count towards the overall planned subject number of 1271.

2.4 DATA ANALYSES

The analysis population for the primary endpoint in the registry will be the intention-to-treat (ITT) population. This population analysis will include all subjects who provided informed consent, met the enrollment criteria, and completed the five year follow-up period or exited the trial early with a primary endpoint event.

Descriptive statistics will be used to present and summarize the data collected in the clinical study. Frequency distributions and cross tabulations will be presented for discrete variables. Means, standard errors, and ranges will be presented for continuous variables.

2.4.1 Endpoint Analysis

Primary safety endpoint 1 will be evaluated by performing an exact binomial test comparing the observed proportion (overall AE-free rate at 5 years) to 92.5%. The lower bound of the 95% confidence interval must be greater than 92.5%.

The evaluation of secondary safety endpoint 1 will be based on the exact, two-sided 95% confidence interval for the observed, individual AE rates at 5 years. Secondary endpoints 2 and 3, which summarize pacing thresholds, sensing, impedance measurements and shock impedance measurements for the Plexa lead, will be reported via standard measures, which can include means, standard deviations, medians, minimums, and maximums.

Secondary endpoint 4, which includes AEs that were excluded from primary safety endpoint 1, through 5 years post-implant will also be summarized as AE rates together with their associated, exact 95% confidence intervals.

2.4.2 Trend Analyses

The primary safety endpoint is evaluated at 5 years post-implant against pre-specified performance levels (92.5% for overall freedom from Plexa lead-rated AEs). To monitor the ongoing incidence of any potential AEs against the accumulating follow-up exposure post-implant, Kaplan-Meier survival curves may be prepared at the reporting intervals for Primary Endpoint 1. Root causes for any failures, regardless of the incidence rates, may be investigated.

2.4.3 Missing Data

All possible steps will be taken to minimize missing data in the registry. This includes but is not limited to monitoring of registry electronic case report forms (eCRFs) for completeness and supporting efforts to track and maintain contact with registry subjects during the follow-up period.

The reasons for any missing data in the registry should be documented. BIOTRONIK Home Monitoring[®] can provide daily automatic sensing values, pacing thresholds, shock impedance, and pacing impedance, depending on the device programming. When available, missing data will be imputed with BIOTRONIK Home Monitoring[®] values obtained from the day of a completed follow-up, target date of a missed follow-up, or the next closest day in the visit window.

For evaluation of primary endpoint1, only subjects who achieve 5 years of follow-up or have experienced an adverse event prior to 5 years will be included in the final evaluation of the associated hypotheses. The secondary endpoints 1 and 4 of other AEs at 5 years will be analyzed in a similar manner. There will be no imputation for these missing adverse event outcomes.

For purposes of the final report Kaplan-Meier survival analyses, all AE data on enrolled non-replaced subjects will be included with follow-up times censored at the time of exit or last completed study visit representing the time of the last known AE status.

Secondary endpoints 2 and 3, which include pacing thresholds, sensing, pacing impedance, and shock impedance measurements will be summarized by scheduled visit through the 5 years of registry follow-up

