2.1 REGISTRY ENDPOINTS

This registry includes the assessments of one primary safety endpoint related to the Plexa lead and several secondary endpoints that evaluate the safety and effectiveness of the Plexa system.

2.1.1 Primary Endpoint 1

The purpose of primary endpoint 1 is to evaluate the overall incidence of adverse events related to the Plexa lead (as defined in Section 9) from implant through 5 years. Assuming that the expected Plexa lead adverse event rate at 5 year post-implant (proportion of subjects with at least one AE in the timeframe from implant through 5 year post-implant) is 7.5% or less, then the primary safety endpoint will be evaluated in the following testable hypothesis in superiority format.

H_0 : The adverse event-free rate (AEFR) for subjects receiving the Plexa lead at 5 years post-implant is less than or equal to 92.5%

$$AEFR \leq 92.5\%$$

H_a : The adverse event-free rate (AEFR) for subjects receiving the Plexa lead at 5 year post-implant is greater than 92.5%

$$AEFR > 92.5\%$$

If the two-sided, 95% lower confidence bound is greater than 92.5%, then the null hypothesis will be rejected.

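### The primary binomial test keeps early exits only if they had an event, so it understates 5-year AE-freedom and does not have the stated 80% power

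*Combined protocol and SAP*

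**What the plan says.** Section 2.1.1 sets the hypothesis on the 5-year AE-free rate, with the AE rate defined as the "proportion of subjects with at least one AE in the timeframe from implant through 5 year post-implant". The null value is 92.5%.

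Section 2.4 states: "The analysis population for the primary endpoint in the registry will be the intention-to-treat (ITT) population". It then limits that population to eligible, consented subjects who "completed the five year follow-up period or exited the trial early with a primary endpoint event". Section 2.4.3 repeats the restriction ("only subjects who achieve 5 years of follow-up or have experienced an adverse event prior to 5 years will be included"), rules out imputation and applies a similar approach to secondary endpoints 1 and 4. Section 2.4.1 tests this set with an exact binomial test.

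Section 2.3 requires 750 evaluable leads for 80% power at a true 95.0%, one-sided alpha 0.025. It reaches 1271 by "Assuming a 10% loss to follow-up rate per year over 5 years of follow-up". Section 2.3.1 adds that "a maximum loss to follow-up of 10% per year (41% over 5 years) was assumed" and that "The attrition rate encompasses all causes for subject exits prior to study completion". Section 2.3.2 describes the same 10% as expected.

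Kaplan-Meier curves appear in Sections 2.4.2 and 2.4.3 for trend monitoring and the final report. They do not decide the hypothesis.

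**The concern.** Inclusion in the primary test depends on the outcome. Early exits lose their event-free members and keep those with events. The resulting proportion is not the one in Section 2.1.1, and the set is not intention-to-treat: it is completers plus early events. The sample size treats attrition only as a loss of numbers, although under this rule it also shifts the success probability.

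This is the registry's only formal test. A lead that performs exactly as assumed could fail it, and the reported AE rates, including those for secondary endpoints 1 and 4, would be too high.

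Section 9.2 adds an ambiguity by expressing AE rates over total subjects. Read with Sections 2.4 and 2.4.3, this most naturally means the same analysis set. An all-enrolled denominator would bias the result the other way.

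**Working it through.** **The plan's own figure.** With n = 750 and a goal of 92.5%, the exact test passes with at least 708 AE-free subjects (at most 42 with an event). Its size is 0.0247 and its power at 95.0% is 0.801. 750/0.9^5 = 1270.1, rounded up to 1271. The plan's arithmetic is right for a plain binomial sample.

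**Inputs from the plan.** N = 1271; true 5-year AE-free rate 95.0%; 10% attrition per year, so 0.9^5 = 0.59049 retained.

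**Assumptions, not in the documents.** Exits are independent of events. The base case has a constant AE hazard λ = −ln(0.95)/5 = 0.01026 per year.

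**Reading A: exits come on top of events.** The exit hazard is μ = −ln(0.9) = 0.10536 per year.
- P(event-free completer) = 0.95 × 0.59049 = 0.5610, or 713.0 subjects.
- P(event before exit) = λ/(λ+μ) × (1 − 0.5610) = 0.0887 × 0.4390 = 0.0390, or 49.5 subjects.
- Expected AE-free proportion = 713.0/762.5 = 93.5%.

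**Reading B: the 10% already covers every exit, as Section 2.3.1 suggests.**
- Event-free completers = 0.59049 × 1271 = 750.5.
- P(event before exit) = (0.01026/0.10536) × (1 − 0.59049) = 0.0399, or 50.7 subjects.
- Expected AE-free proportion = 750.5/801.2 = 93.7%.

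With 750 subjects the test needs an observed 708/750 = 94.4%. Both expected values lie below that mark.

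**Power**, exact and averaged over the random evaluable n, with Weibull event timing:

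| Event timing | Reading A | Reading B |
|---|---|---|
| Shape 0.5 (early) | 6% | 10% |
| Shape 1 (constant) | 16% | 22% |
| Shape 2 | 35% | 42% |
| Shape 3 (late) | 47% | 53% |

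Simulation of the constant-hazard case gave 16.2% (A) and 22.0% (B). Over any event timing and any independent exit pattern with 59% retained, power lies between 0.3% and 78% (A) or 0.9% and 80% (B). The top needs every event at year 5 or every exit at implant.

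**Other inputs**, constant hazard, A / B:
- 5% attrition per year: 61% / 70%. At 3%: 79% / 86%.
- True rate 96.0% at 10% attrition: 70% / 76%. True rate 96.5%: 91% / 94%.

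**Direction.** At a true 92.5% and 10% attrition, the rejection probability is at most about 0.002 over the four shapes.

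**All-enrolled reading of Section 9.2.** With n = 1271 the test passes with at most 76 events. A lead at a true 92.5% would then pass 61% / 48% of the time with a constant hazard.

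**Kaplan-Meier on the same 1271 subjects.** With a log-log 95% limit, simulated power is about 83% to 92% over the shapes, and size stays below 0.025. The untransformed Greenwood limit has size 0.033 to 0.040, so the type of interval must be specified.

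**Secondary endpoint 4.** An assumed true peri-implant rate of 2.0% would be reported as 0.02/(0.02 + 0.98 × 0.59049) = 3.3%.

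**The case against.** **The 16% to 22% is one scenario.** True. Section 2.3.1 calls 10% a maximum, and the predecessor data hint at later or rarer events. In Section 1.3.2, Protego had 1 primary AE in 1305. At an assumed mean follow-up of 6 to 10.5 months, a 5% five-year rate predicts 7 to 12 events with a constant hazard but only 1 to 2 with shape 2. In Section 1.3.1, GALAXY had 61 events. Assuming uniform enrollment and 10% exits per year, a true 95.0% at day 1809 predicts about 76 (constant), 67 (shape 2) or 62 to 63 (shape 3). Section 9.3.1 also removes dislodgements and threshold or capture problems within 30 days, which makes very early timing less plausible. None of this is decisive: GALAXY's standard error is 1.0%, 15% to 20% exits per year would fit a constant hazard (67 to about 60 events), and its primary endpoint left out dislodgements up to 180 days. Later timing raises power to 35% to 53%, not to 80%.

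**The 95.0% may have been meant for the evaluable set.** The sample size would then be coherent, and the fault would be an unstated estimand. Section 2.3 gives no source for the figure. It equals GALAXY's Kaplan-Meier estimate, and Section 2.1.1 speaks of all subjects from implant, so this reading is less likely.

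**The error is conservative, the leads are already marketed, and Kaplan-Meier is planned anyway.** All true. The cost falls on power and on the accuracy of reported rates. The Kaplan-Meier curve would expose the discrepancy but would not settle the test. The safety reassurance also holds only if Sections 2.4 and 2.4.3 govern the denominator in Section 9.2.

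**Kaplan-Meier is one valid choice among others.** This stands. Restating the power of the present test is an acceptable minimum.

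**Conclusion.** The concern holds. The analysis set in Sections 2.4 and 2.4.3 does not estimate the rate in Section 2.1.1 and is not the sample that Section 2.3 powers. With the plan's inputs, independent exits and a constant AE hazard, power is about 16% to 22%; over the event timings tried it is 6% to 53%. In seven of the eight timing and attrition combinations tabulated, a lead at exactly 95.0% would more likely fail than pass. The downward bias does not depend on the timing chosen, as long as some events precede year 5 and some subjects exit. Its size does depend on timing, attrition and the true rate. Power near or above 80% needs attrition of about 3% per year, a true rate of about 96.1% to 96.2% (constant hazard), or nearly all events at the end of follow-up.

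**What to change.** - In Sections 2.4, 2.4.1 and 2.4.3, base the primary decision on the 5-year Kaplan-Meier AE-free probability in all enrolled eligible subjects. Censor event-free exits, including replaced subjects, at exit.
- Reject the null if the lower limit of the two-sided 95% interval exceeds 92.5%. Name an interval that holds its size, for example Greenwood with a log-log transformation.
- Use the same approach for the 5-year rates in secondary endpoints 1 and 4, and align the denominator in Section 9.2.
- Remove the intention-to-treat label from the completer set and keep that binomial analysis only as a sensitivity analysis.
- Restate power in Section 2.3 with its timing and attrition assumptions.
- Name the estimand and add a sensitivity analysis with death as a competing event.

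The cost is protocol wording, with no extra subjects or data. The decision would then rely on independent censoring, including for deaths and explants, which the calculations above assume and do not prove. The choice of estimand matters: with a constant hazard (Reading A), the AE-free figure with death as a competing event is 95.6% if half of exits are deaths and 96.1% if all are (assumed shares), against 95.0% with deaths censored.

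If the binomial test stays primary, its power should be restated as above. Reaching 80% with it would need roughly 6,000 (Reading B) to 8,700 (Reading A) enrolled, at a constant hazard and 10% attrition per year.

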9.2 ENDPOINT ANALYSIS

All protocol defined adverse events included in the primary and secondary endpoint analysis will be adjudicated by the Clinical Events Committee (CEC) (see Section 2.1, Section 6.2, and section 9.3). For each adverse event, the CEC will indicate whether the adverse event relatedness to the Plexa lead is: not related, related, possibly related, or unknown.

In evaluation of primary endpoint 1 and secondary endpoint 1 for the registry, the estimates of AE rates will be based on the number of subjects with at least one “related” AE as a proportion of total subjects. Subjects with a final adjudicated related AE classification of “possibly related”, “not related” or “unknown” will not have that individual event contribute to or be included in the evaluation of primary safety endpoint. The same rules will be used for purposes of Kaplan-Meier survival analyses, described in Section 2.4.2.

Secondary endpoint 4, which includes AEs that were excluded from primary safety endpoint 1 through 5 years post-implant, will also be summarized as AE rates along with their associated, exact 95% confidence intervals.

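### Secondary endpoints 1 and 4: the 5-year rates leave out AE-free early exits, so the descriptive AE rates are biased upward by an amount that depends on attrition

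*Combined protocol and SAP*

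**What the plan says.** Section 2.4.3 keeps in the primary endpoint 1 evaluation only subjects with 5 years of follow-up or an earlier adverse event. It continues "The secondary endpoints 1 and 4 of other AEs at 5 years will be analyzed in a similar manner" and rules out imputation of missing AE outcomes. Section 2.4 describes the primary population in similar terms: those who "completed the five year follow-up period or exited the trial early with a primary endpoint event".

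Section 2.4.1 gives secondary endpoints 1 and 4 exact 95% intervals and names no other denominator. Section 9.2 bases primary endpoint 1 and secondary endpoint 1 on subjects with at least one related "AE as a proportion of total subjects", without defining that total.

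On follow-up, section 2.3.1 says "a maximum loss to follow-up of 10% per year (41% over 5 years) was assumed" and "The attrition rate encompasses all causes for subject exits prior to study completion". Section 2.3.2 says "A drop-out rate of 10% of subjects per year is expected in the Plexa Registry". Censored estimates appear in section 2.4.2 ("Kaplan-Meier survival curves may be prepared at the reporting intervals for Primary Endpoint 1") and in section 2.4.3, where the final-report Kaplan-Meier set leaves out replaced subjects. Neither section makes a censored estimate the basis for the secondary AE rates.

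Section 9.3.1 sends dislodgements, high thresholds and capture failures up to 30 days after implant or lead revision to endpoint 4. Section 9.3.2 adds all major implant procedure-related AEs.

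**The concern.** Membership of the denominator depends on the outcome. A subject with an AE on day 5 is always counted. A subject seen to be AE-free through day 30 who leaves in year 3 is not, although that subject's 30-day outcome is fully known. The rate therefore rises with attrition even if the lead and the procedure perform identically. The distortion is greatest for AEs close to implant, for which 5-year completion matters least.

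At stake is the descriptive safety profile: the rate of each AE type and its interval. An exact binomial interval reflects sampling error only and does not correct this selection.

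**Working it through.** **The plan's own figures.** 0.9^5 = 0.5905, so 5-year attrition is 1 − 0.5905 = 41%. 750 / 0.5905 = 1270.1, rounded up to 1271. Both match sections 2.3 and 2.3.1.

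**Inputs.** N = 1271. Annual attrition a = 10% (sections 2.3.1 and 2.3.2); a = 5% and other lower values are assumptions. Retention S = (1 − a)^5, which is 0.5905 at 10% and 0.7738 at 5%. Exits are taken as independent of AEs. The share s of exits that are deaths is not given, so s = 0, 0.5 and 1 are shown.

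**AEs within 30 days of the initial implant.** With true rate r, reported rate = r / (r + S(1 − r)). For rare AEs the inflation is close to 1/S:

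- 10% per year: 1/0.5905 = 1.69
- 5% per year: 1/0.7738 = 1.29

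At 7% and 3% per year the factors are 1.43 and 1.16. They shrink for common AEs: 1.64 at r = 5% and 10% per year.

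Illustration: Protego dislodgement within 30 days, 7/1305 = 0.54% (section 1.3.2, Table 3). Expected events are 1271 × 0.0054 = 6.9. Expected AE-free completers at 10% per year are (1271 − 6.9) × 0.5905 = 746.5. The reported rate is 6.9 / (6.9 + 746.5) = 0.91%. In 200,000 simulated registries the nominal 95% Clopper-Pearson interval covered the true 0.54% in about 77% at 10% per year and 91% at 5%.

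**AEs accruing evenly over 5 years.** Let c = −ln(1 − a) and let h be the constant AE hazard.

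- True cumulative incidence, death competing: h/(h + sc) × (1 − exp(−5(h + sc)))
- Observed: h/(h + c) × (1 − exp(−5(h + c)))
- AE-free completers: exp(−5(h + c))
- Reported under section 2.4.3: observed / (observed + completers)

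For small h at 10% per year (c = 0.1054), observed ≈ 3.887h and reported ≈ 3.887h / 0.5905 = 6.58h. The true value is about 5h with no deaths, 4.40h with half and 3.887h with all. Results at a true rate of 0.54%:

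| Attrition | No deaths | Half deaths | All deaths |
|---|---|---|---|
| 10%/yr | 1.31 | 1.49 | 1.69 |
| 5%/yr | 1.14 | 1.21 | 1.29 |

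Coverage at 10% per year (100,000 simulations) is 92/86/77% at a true rate of 0.54%, and 89/78/63% at 1.05%, the GALAXY noise or oversensing rate (section 1.3.1, Table 1).

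**If the total in section 9.2 meant all enrolled.** Evenly accruing endpoint 1 AEs would be reported at observed / true = 3.887/5 = 0.78, 3.887/4.40 = 0.88 and 1.00 of the true value at 10% per year.

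**Replacement.** Under the section 2.4.3 rule an AE-free exit leaves the denominator whether or not it is replaced. Each replacement adds r to the numerator and r + S(1 − r) to the denominator in expectation, the same ratio as any other subject. Simulation of the 0.54% early AE at 10% per year gave 0.91% without replacement and 0.90% with half of the AE-free exits replaced.

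**The case against.** The strongest reply is that little hangs on this. Neither endpoint has a hypothesis test (section 2.1.2), the bias runs against the lead, and the illustration moves a rate by only 0.37 percentage points (0.91 − 0.54). That stands, and it limits the severity. It does not make the rates correct.

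Several stronger readings are tempting, but the documents do not support them:

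- **Replacement makes it worse.** Because "Subjects who have had a protocol defined adverse event will not be replaced", a reader might infer that replacing AE-free exits adds to the inflation. Under the section 2.4.3 rule it does not, as shown above. Replaced subjects matter only because the Kaplan-Meier set leaves them out.
- **Evenly accruing AEs are overstated 1.69-fold.** That needs every exit to be a death. Section 2.3.2 also lists explants, withdrawals and loss of contact.
- **The Protego figure predicts Plexa.** It does not. Those events were reported as possibly related, and section 1.3.2 says no secondary AE was adjudicated as related. Whether possibly related Plexa events count in endpoint 4 is not stated.
- **The plan contradicts itself on the denominator.** Section 9.2 covers primary endpoint 1 in the same sentence, and that population is restricted elsewhere. Its total most coherently means the restricted subset. The term is undefined rather than clearly in conflict.

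One could also argue that the section 2.4 population was meant for endpoint 4. It is defined for the primary endpoint only. Using it would largely remove the inflation of early endpoint 4 rates, but would discard about 41% of the early events (2.8 of the 6.9 expected above).

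**Conclusion.** The concern holds as a bias in descriptive rates. Following section 2.4.3 as written overstates early AEs about 1.69-fold at 10% attrition per year and 1.29-fold at an assumed 5%. It overstates evenly accruing AEs by 1.31 to 1.69 and 1.14 to 1.29 respectively, depending on the unknown death share. Section 2.3.1 presents 10% as a ceiling and section 2.3.2 as the expectation, so the actual size could be smaller.

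The factors assume rare AE types, constant attrition and exits unrelated to AEs. No test decision changes and the bias cannot make the lead look safer. The plan should still be changed: the rates would partly measure attrition, and no section supplies a censoring-adjusted estimate for these endpoints.

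**What to change.** Replace the sentence on secondary endpoints 1 and 4 in section 2.4.3 and align section 9.2 with it.

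1. For each AE type, report the 5-year cumulative incidence (Aalen-Johansen) of the first event on all enrolled subjects, including those later replaced. Measure time from implant, censor at exit or last known AE status, treat death as a competing event, and give a log-log 95% interval.
2. For AEs within 30 days of the initial implant, a simple events-over-all-enrolled proportion with an exact interval may be used. With zero events the upper bound is 1 − 0.025^(1/1271) = 0.29%. Describe it as conditional on enrolment with the study system, because section 3.2.3 collects AEs only for the system in place at consent. At 10% per year about 1271 × (1 − 0.9^(30/365)) = 11 subjects would exit before day 30.
3. Do not extend that shortcut to later procedure-related AEs, such as infection or pocket dehiscence, which section 9.1.1 does not limit in time. Spread evenly over 24 months, they would be reported at (1 − 0.81)/(2 × 0.1054) = 0.90 of the true rate at 10% per year with no deaths.
4. For other AE types with zero events, give an exact upper bound from the number followed to 5 years (1 − 0.025^(1/750) = 0.49% at n = 750), labelled conservative.

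The cost is wording and minor programming. The drawback is that endpoint 1 component rates will no longer reconcile with the completer-based primary rate. The report should say so, and may show the section 2.4.3 proportion alongside for traceability.

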6.2 CLINICAL EVENTS COMMITTEE

A Clinical Events Committee (CEC) consisting of at least 3 independent electrophysiologists will review and adjudicate adverse events that occur during the registry. The CEC will be blinded to the clinical registry site and subject identity, and to minimize bias, members will not participate as investigators. The CEC will create a registry specific charter defining the adverse event adjudication process, specifically detailing review guidelines along with appropriate response timelines.

All protocol defined adverse events included in the primary and secondary endpoint analysis (see Section 9.3.1 and Section 9.3.2) will be adjudicated by the CEC. The CEC will indicate whether the adverse event is related, possibly related, not related, or has an unknown relation to the Plexa lead. The CEC will have the responsibility to adjudicate the classification of each reported adverse event as implant procedure, implanted pulse generator, lead, or non-procedure non-system related, to adjudicate the category of AE (e.g. Plexa lead dislodgement, major hematoma, etc.), and to assess the seriousness of each AE.

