9.3 ADVERSE EVENTS FOR THE ANALYSIS OF THE PRIMARY AND SECONDARY ENDPOINTS

9.3.1 Adverse Events for the Analysis of Primary Endpoint 1 and Secondary Endpoint 1

If any of the following invasive interventions occur in order to resolve an above listed Plexa lead-related AE, the AE will be included in the primary safety endpoint analysis:

- Lead surgically repositioned
- Lead surgically explanted
- Lead surgically replaced
- Lead surgically abandoned
- Other lead-related surgery performed

Additionally, if any of the following non-invasive interventions occur in order to resolve an above listed Plexa lead-related AE, the Plexa lead-related AE will be included in the primary endpoint analysis:

- Lead pacing polarity or pacing mode reprogrammed in response to a problem with the mechanical or electrical integrity of the lead
- Lead programmed off in response to a problem with the mechanical or electrical integrity of the lead
- Lead use continued based on medical judgment despite a known clinical performance issue

AEs that are corrected by reprogramming the pulse generator (other than the above) and resolved without invasive intervention will not be considered an adverse event. For example, electrical reprogramming of the pacing polarity to eliminate extracardiac stimulation will not be considered an adverse event if not in response to a problem with the mechanical or electrical integrity of the lead. Similarly, increasing pacing output as a result of an elevated threshold without further intervention will not be considered an adverse event.

Subject deaths as a result of a Plexa lead-related AE will be included in the primary endpoint analysis.

Primary endpoint 1 and secondary endpoint 1 will exclude 1) lead dislodgements that occur less than or equal to 30 days after lead implant or a lead revision procedure and 2) high pacing threshold, failure to capture, or intermittent capture that occurs less than or equal to 30 days after lead implant or a lead revision procedure. However, these will count towards secondary endpoint 4.

9.3.2 Adverse Events for the Analysis of Secondary Endpoint 4

All major implant procedure-related adverse events are included in the secondary endpoint 4 analysis, as well as Pulse Generator-related and Non-Procedure Non-System-related adverse events that require invasive intervention to resolve.

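### The final-report Kaplan-Meier analysis drops the event-free follow-up of replaced subjects instead of censoring it (minor; small conservative bias)

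*Combined protocol and SAP*

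**What the plan says.** Three provisions of the combined protocol and SAP bear on this.

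- **Replacement (Section 2.3.2).** It covers "subjects who exit the clinical investigation due to death, device explants, subject directed withdrawals, physician directed withdrawals" and loss of contact. Such subjects "may be replaced as long as enrollment is ongoing", so replacement is optional and stops when enrollment closes. There is one bar: "Subjects who have had a protocol defined adverse event will not be replaced". Replaced subjects are left out of the planned 1271.
- **Final-report Kaplan-Meier analysis (Section 2.4.3).** Here "all AE data on enrolled non-replaced subjects will be included with follow-up times censored at the time of exit or last completed study visit". Censoring is applied only within the non-replaced set.
- **Hypothesis test (Sections 2.4.1 and 2.4.3).** Primary Endpoint 1 is decided by an exact binomial test against 92.5%, for which "only subjects who achieve 5 years of follow-up or have experienced an adverse event prior to 5 years will be included".

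No other section brings replaced subjects back into the Kaplan-Meier analysis.

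**The concern.** Kaplan-Meier estimation is built to use a subject's follow-up until exit, and Section 2.4.3 already does this for subjects who leave and are not replaced. For replaced subjects it discards that follow-up altogether. The discarding is not neutral. Of two subjects who leave in month 8, the one with a protocol-defined AE cannot be replaced and stays in. The one without may be replaced, and eight event-free months vanish. The early risk sets shrink while every observed primary event stays, so the estimated AE rate rises.

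At stake is the accuracy of a supportive curve for Primary Endpoint 1 in the final report. Leaving replaced subjects out of the recruitment count is a reasonable enrollment rule, but it gives no reason to leave them out of the analysis.

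**Working it through.** **The plan's own figures.** At n = 750 the exact binomial test needs at least 708 AE-free subjects. Its one-sided alpha is 0.0247, and its power at 95.0% is 80.1%. Attrition gives 750 / 0.9^5 = 1270.1, rounded up to 1271. Both figures reproduce, and neither depends on the Kaplan-Meier set.

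**Inputs from the documents.** Exits of 10% per year (Sections 2.3 and 2.3.1) give an exit hazard λ = −ln 0.9 = 0.1054 per year. A five-year AE-free rate of 95.0% (Section 2.3) gives a cumulative hazard H(5) = −ln 0.95 = 0.0513.

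**Assumed: accrual length A.** The predecessor registries give a pace.

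- Protego (Section 1.3.2): 1695 subjects in about 2.1 years, or 807 per year. 1271 / 807 = 1.6 years.
- GALAXY (Section 1.3.1): 1997 subjects in about 2.8 years, or 713 per year. 1271 / 713 = 1.8 years. With 138 replacements added (derived below), 1409 / 713 = 2.0 years.

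I use A = 1.6 to 2.0 years, with entry uniform over A.

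**Assumed: replacement.** Every eligible exit is replaced (the upper limit), and AE status is final at replacement. Only primary events are modelled. The bar in Section 2.3.2 covers any protocol-defined AE, so the real number removed would be somewhat smaller.

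**Assumed: hazard shape.** Three forms are tried: constant, H(t) = 0.0513·t/5; rising linearly, H(t) = 0.0513·(t/5)²; and front-loaded, with half of H(5) in year 1 and the rest spread evenly over years 2 to 5.

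**Formula.** Let S(t) = exp(−H(t)), G(t) = exp(−λt) and h = H′. An event-free exit at follow-up time u falls within open enrollment with probability 1 − u/A for u < A. Removed subjects who would still have been at risk at t < A are

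R(t) = ∫ from t to A of λ·S(u)·G(u)·(1 − u/A) du, with R(t) = 0 from A on.

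The retained risk set is S·G − R, and the Kaplan-Meier AE rate is

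1 − exp(−∫ from 0 to 5 of h·S·G / (S·G − R) dt).

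With R = 0 this returns 5.000%, which is also the result when replaced subjects are censored at exit.

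**Number removed, constant hazard.** Let c = 0.1054 + 0.0513/5 = 0.1156. The removed fraction is f = (λ/c)·[1 − (1 − e^(−cA))/(cA)]. For A = 1.6, f = 0.079 and 1271·f/(1 − f) is about 110 replaced. For A = 2.0, f = 0.098 and the number is about 138.

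**Kaplan-Meier five-year AE rate, all eligible exits replaced (true rate 5.000%)**

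| Hazard | A = 1.6 | A = 2.0 | Rise, points |
|---|---|---|---|
| Rising | 5.007% | 5.014% | 0.007 to 0.014 |
| Constant | 5.044% | 5.069% | 0.04 to 0.07 |
| Half in year 1 | 5.105% | 5.155% | 0.10 to 0.16 |

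With half of the eligible exits replaced, the constant-hazard rate is 5.021% to 5.033%. A separate simulation with two years of accrual, constant hazard and full replacement gives a difference of 0.07 points with about 138 replaced.

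**Against sampling error.** The Greenwood standard error at n = 1271 is 0.702 points (constant) and 0.732 points (rising), or about 0.7. As a share of one standard error:

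- rising: 0.007/0.732 = 1% to 0.014/0.732 = 2%
- constant: 0.044/0.702 = 6% to 0.069/0.702 = 10%
- half in year 1: 0.105/0.7 = 15% to 0.155/0.7 = 22%

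**The case against.** The strongest case for leaving the text alone is that nothing decisive depends on it. The hypothesis test is the exact binomial, and an event-free early exit is outside that set whether replaced or not. Replacement is optional and limited to open enrollment. The shift is well below one standard error and overstates the AE rate, so it does not flatter the lead. All of this stands, and it is why the point is minor. It gives no reason to prefer deletion, which gains nothing over censoring.

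A reader might infer something stronger: that events are lost and the curve could understate the AE rate. Deaths and explants are replaceable, and under Section 9.3.1 "Subject deaths as a result of a Plexa lead-related AE will be included in the primary endpoint analysis". Section 6.2 adds that "The CEC will indicate whether the adverse event is related, possibly related, not related, or has an unknown relation to the Plexa lead", and Section 9.2 carries the relatedness rule into the curve: "The same rules will be used for purposes of Kaplan-Meier survival analyses, described in Section 2.4.2". So a subject might be replaced and the event adjudicated as related only later. The documents do not support this. The bar in Section 2.3.2 depends on having had a protocol-defined AE, not on the committee's relatedness finding, so a reported AE blocks replacement before adjudication. Table 6 requires AE reports within 10 calendar days, Section 10.2.2 requires an AE form when a death is associated with an AE, and Section 10.2.3 holds the exit after an explant until the revision is documented. What remains is an event first recognised after replacement. The plan does not say whether the replacement would then be undone, and nothing in it indicates how often this would occur.

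Two other inferences should be avoided. GALAXY's 2.8 years is the enrollment time of a 1997-subject registry and would overstate accrual for 1271. Nor can GALAXY rule out early clustering of events: its primary endpoint left out dislodgements up to 180 days (Table 1), whereas Plexa's exclusion stops at 30 days (Section 9.3.1). The front-loaded case therefore stays in the range.

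**Conclusion.** The point holds as a minor wording defect. Read together, Sections 2.3.2 and 2.4.3 remove event-free follow-up by a rule that depends on outcome, and the reported Kaplan-Meier AE rate is biased slightly upward. At the upper limit of full replacement, the bias runs from under 0.01 to about 0.16 points across the three hazard shapes, less than a quarter of one standard error. It shrinks with the share replaced. These sizes rest on the assumed accrual length, uniform entry and the planned exit and AE rates; the direction requires only that AE status is final at replacement. The primary test and the 750 and 1271 figures do not change. The event recognised after replacement is a gap in the text, not evidence of bias in the other direction.

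**What to change.** Reword the Kaplan-Meier sentence in Section 2.4.3 so that the analysis takes in AE data on all enrolled subjects, whether or not they were replaced, censored at exit or last known AE status. State that replacement affects only the recruitment count. This removes the bias and also settles the event recognised after replacement, because the subject would be in the analysis anyway. The cost is one sentence: the data are already collected up to exit, and no change to sample size or to the primary test follows.
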